9.4.7. Subjective Grading of Comfort/Tolerability

Subjective comfort/tolerability data (i.e., rating of drop comfort as assessed by the subject) will be collected at each post baseline visit (≥ 10 minutes after the IOP measurement). Consult the Study Manual for specific details.

9.5. Adverse and Serious Adverse Events

9.5.1. Definition of Adverse Events

9.5.1.1. Adverse Event (AE)

An AE is any untoward medical occurrence in a patient or clinical study subject administered a study medication (pharmaceutical/biological product) that does not necessarily have a causal relationship to this medication. An AE can therefore be any unfavorable and unintended sign (including abnormal laboratory findings), symptom, or disease temporally associated with the use of the study medication, whether or not related to the study medication. Study medication includes the investigational drug under evaluation and the comparator product or vehicle placebo that is given during any phase of the study.

Adverse events are collected from the time the subject signs the ICF through the final study visit. Medical conditions/diseases present before starting the investigational treatment are only considered AEs if they worsen any time after the subject signs the ICF. Abnormal test results constitute AEs only if they induce clinical signs or symptoms or require therapy.

The occurrence of AEs should be sought by open-ended questioning of the subject at each visit during the study. At each clinic visit, study personnel should ask the following question: "Have you had any problems since your last visit?" AEs also may be detected when they are volunteered by the subject during or between visits or through study assessments.

9.5.1.2. **Serious Adverse Event (SAE)**

An SAE is any untoward medical occurrence that at any dose:

- Results in death,
- Is life-threatening,

Note: The term "life-threatening" refers to an event in which the subject was at risk of death at the time of the event; it does not refer to an event which hypothetically might have caused death if it were more severe.

- Results in persistent or significant disability/incapacity (excluding progression/outcome of the disease under study),
- Is a congenital anomaly/birth defect,
- Requires inpatient hospitalization or prolongation of existing hospitalization, or
- Is medically significant, i.e., defined as an event that jeopardizes the health of the subject or may require medical or surgical intervention to prevent one of the outcomes listed above.

Treatment on an outpatient emergency basis that does not result in hospital admission, or a hospitalization that is elective or is a preplanned treatment for a pre-existing condition that is unrelated to the indication under study and has not worsened since the start of the study, is not considered an SAE.

All SAEs that are ongoing at the time of completion or discontinuation from the study will be followed until stabilization or resolution of the event.

9.5.2. **Relationship to Study Drug**

The relationship of AEs to the study medication should be assessed by the Investigator using the definitions below.

Not related: The temporal relationship of the event to the study medication makes a causal relationship unlikely, or other drugs, therapeutic interventions or underlying conditions provide a sufficient explanation for the observed event.

Related: The temporal relationship of the event to the study medication makes a causal relationship possible or other drugs, therapeutic interventions or underlying conditions do not provide a sufficient explanation for the observed event.

If there is any valid reason, even if undetermined, for suspecting a possible cause-and-effect relationship between the study medication and the occurrence of the AE, then the AE should be considered "related."

If the relationship between the AE/SAE and the investigational product is determined by the Sponsor to be "related," the event will be considered related to the investigational product for the purposes of expedited regulatory reporting.

9.5.3. Recording Adverse Events

Adverse events spontaneously reported by the subject and/or in response to an open question from the study personnel or revealed by observation, regardless of severity or potential association with the study medication or study procedures, will be recorded in the eCRF. Changes from baseline assessments that are part of the disease being studied will not necessarily be recorded as AEs unless the Investigator deems them as such. Clinically significant changes in BP and HR should be reported as AEs. All AEs that occur following consent and until the final study visit (Visit 6/Day 84) should be collected and recorded on the AE eCRF page. Serious adverse events will be followed until the event is resolved or stabilized.

The AE term should be reported in standard medical terminology when possible. For each AE, the Investigator will evaluate and report the following:

- Onset (date)
- Resolution (date)
- Severity grade (mild, moderate, severe)
- Relationship to study medication (not related, related)
- Action taken regarding study medication (none, study medication temporarily interrupted, study medication permanently discontinued)
- Action taken regarding the event (concomitant medication taken; hospitalization/prolonged hospitalization; other)
- Serious (yes/no)

The severity grade should be determined by the Investigator using the definitions below.

- Mild: Discomfort noticed but no disruption of normal daily activity
- Moderate: Discomfort sufficient to cause interference with normal daily activity
- Severe: Incapacitating, with inability to perform normal activities

It is important to distinguish between serious and severe AEs. Severity is a measure of intensity (as defined directly above) whereas seriousness is defined by the criteria under Section 9.5.1.2. An AE of severe intensity may not be considered serious.

Should a pregnancy occur, it must be reported and recorded on the pregnancy form. Pregnancy is not regarded as an AE unless there is a suspicion that an investigational product may have interfered with the effectiveness of a contraceptive medication. The subject will be withdrawn from study medication and followed through conclusion of pregnancy. The outcome of all pregnancies (spontaneous miscarriage, elective termination, normal birth, or congenital abnormality) must be followed up and documented.

9.5.4. Reporting Adverse Events

All SAEs (related and unrelated) will be recorded following consent and until the final study visit, Visit 6/Day 84, following the end of treatment exposure. Any SAEs suspected to be related to the investigational product should be reported.

Any SAE that occurs must be reported to Trial Runners, the CRO, within 24 hours of its occurrence or within 24 hours of learning of its occurrence. Recurrent episodes, complications, or progression of the initial SAE must be reported to Trial Runners as follow-up to the original episode within 24 hours of the Investigator receiving the information. Information about all SAEs will be collected and recorded on the SAE form. All pertinent medical records and information collected during the treatment and follow-up of the subject should be maintained at the site with a copy emailed to [contact]. The Investigator must assess the SAE relationship and complete and sign the SAE form. Trial Runners/the Sponsor may request additional information. Follow-up information (e.g., discharge summary) will be retained in the subject's chart and a copy will be emailed to [contact].

In addition, all SAEs should be recorded on the Adverse Event eCRF page with the serious question marked "Yes".

It is the Investigator's responsibility to notify the approving IRB of any SAEs on a timely basis as instructed by the Sponsor following the Sponsor's determination of causality.

All subjects who experience an SAE should be followed clinically and undergo the appropriate diagnostic evaluations until stabilization or resolution of the event.

The Sponsor will report all SAEs to the US Food and Drug Administration (FDA) on the appropriate schedule depending if the event is drug related or not drug related, expected or unexpected (based on the available information in the Investigator's Brochure).

Any death occurring during the study and follow up period should be reported as an SAE. For any death occurring through the end of the study, regardless of the degree of relationship to study medication, the SAE resulting in the death must be reported to Trial Runners. A death occurring after completion of the study does not require completion of the SAE form.

10. STUDY ACTIVITIES

Table 2 provides a tabular summary of all scheduled visits and procedures to be performed during the clinical study. Ophthalmic procedures should be performed in the order in which they are shown in the Schedule of Procedures. Please note that per Section 10.1.1, procedures performed at Visit 1/Screening may be split and conducted at a separate visit (preferably within 1 week after Visit 1) to be scheduled before Visit 3/Qualification/Baseline/Day 1.

10.1. Screening Visit

Screening eligibility assessments are obtained during the Screening Visit conducted on or between Day -35 to -1 (Visit 1), which is dependent on the required washout period for prior ocular hypotensive medications.

10.1.1. Visit 1/Screening (Day -35 to -1)

At Visit 1/Screening, (Day -35 to -1), subjects will provide informed consent before any study-related procedures are conducted. Subjects will then participate in screening procedures to establish eligibility for the study.

If necessary, Visit 1 may be split and a separate visit (preferably within 1 week after Visit 1) may be scheduled to allow all required screening procedures to be performed before Visit 3/Qualification/Baseline. For example, if dilated ophthalmoscopy is not performed because the subject prefers not to be dilated at this visit, the subject may return on another day. Also, if the VF performed at or within 90 days prior to Visit 1 does not meet study required parameters, it may be repeated (test should be prior to randomization at Visit 3/Qualification/Baseline).

At the end of the visit/split visit, inclusion/exclusion criteria will be reviewed. Eligible subjects will begin the washout period that is required for the ocular hypotensive medication the subject was receiving or, if medication naïve, be scheduled for Visit 3/Qualification/Baseline.

Screening procedures include the following:

- Informed consent/assent
- Demographics
- Medical and ophthalmic histories
- Prior and concomitant medications/therapies
- Urine pregnancy test (females of childbearing potential only)
- BP/HR
- BCVA (logMAR)
- Biomicroscopy
- IOP
- Visual field test (may be performed at any time during the Screening visit prior to dilation for ophthalmoscopy, or within 90 days prior to Screening)
- Gonioscopy (may be performed during the Screening visit at any time after IOP and before dilation for ophthalmoscopy, or within 90 days prior to Screening)
- Pachymetry (may be performed during the Screening visit at any time after IOP, or within 90 days prior to Screening)
- Dilated ophthalmoscopy
- Review eligibility criteria
- Provide instructions regarding the washout period

10.2. Washout Period

A washout period will occur for all subjects using ocular hypotensive medications at Screening. If required, subjects will participate in a minimum washout period of 28 days for prostaglandin analogs, ROCK inhibitors, or β -blockers, 14 days for adrenergic agonists, and 5 days for muscarinic agonists or CAIs.

10.2.1. Visit 2/Optional Washout Safety Check (Day -14 ± 3)

A mid-washout onsite safety check may be conducted for subjects undergoing a 28-day washout period, at the Investigator's discretion.

Procedures performed at Visit 2 include the following:

- AE assessment
- Concomitant medication review

- BCVA
- IOP

10.3. Qualification Visit

One qualification visit will be conducted, Visit 3/Qualification/Baseline/Day 1.

At Visit 3, subjects must have unmedicated IOP measurements in at least one eye ≥ 22 and ≤ 34 mm Hg at 8:00 AM and ≥ 18 and ≤ 34 mm Hg at 10:00 AM and 4:00 PM (each timepoint is ± 30 minutes). The IOP must be at least 22 mm Hg at each consecutive measurement at the 8:00 AM time point.

10.3.1. Visit 3/Qualification/Baseline/Day 1

This visit will be scheduled so that IOP can be taken at 8:00 AM, 10:00 AM, and 4:00 PM (\pm 30 minutes). If the subject has not discontinued using their prior ocular hypotensive medications for the required washout period duration (28 days for prostaglandin analogs, ROCK inhibitors or β -blockers, 14 days for adrenergic agonists, and 5 days for muscarinic agonists or CAIs), the visit will need to be rescheduled.

Procedures performed at Visit 3 include the following:

8 AM (± 30 minutes):

- AE assessment
- Concomitant medication review
- Urine pregnancy test (females of childbearing potential only); must be performed prior to randomization
- BCVA
- Grading conjunctival hyperemia (grading of conjunctival hyperemia must be performed prior to randomization)
- Biomicroscopy/
- IOP

10 AM (± 30 minutes):

- AE assessment
- HR/BP
- Biomicroscopy
- IOP

4 PM (± 30 minutes):

- AE assessment
- Biomicroscopy

- IOP
- Review eligibility criteria
- Randomize eligible subjects
- Dispense study medication
- Provide instruction and supervise guided practice of drop instillation by subject/caretaker (no evening dose should be administered at home after this visit)
- Conduct drop comfort rating following instillation of study medication (≥ 10 minutes after the IOP measurement)
- Study medication accountability (i.e., document that Kit 1 was dispensed)

10.4. Treatment Visits

These treatment visits (Visit 4/Day 15, Visit 5/Day 42, and Visit 6/Day 84), will be scheduled so that IOP can be taken at 8:00 AM, at 2 hours after the dosing of study medication at the clinical site (\sim 10:00 AM), and at 4:00 PM (each ± 30 minutes).

Subjects should be reminded before each visit not to dose in the morning before coming to the site and to bring their box containing all study medication materials (opened and unopened bottles/vials and pouches) to the study site for drug accountability/treatment compliance assessment. When the subject arrives, confirm that the previous day's evening dose of study medication *was* administered, and the morning dose of study medication *has not* been administered. Subjects who did not dose the evening before or who dosed prior to the morning visit MUST be rescheduled, even if the next appointment is out of window.

10.4.1. Visit 4/Day 15 ± 3

Procedures performed at Visit 4 include the following:

8 AM (± 30 minutes):

- AE assessment
- Concomitant medication review
- BCVA
- Grading conjunctival hyperemia
- Biomicroscopy
- IOP
- Drop instillation (should occur as close as possible to 15 minutes after IOP measurement, but not before 10 minutes after IOP measurement)
- Conduct drop comfort rating following instillation of study medication (≥ 10 minutes after the IOP measurement)

2 hours ± 30 minutes after drop instillation:

- AE assessment
- HR/BP
- Biomicroscopy
- IOP
- Blood collection for pharmacokinetics (PK) assessment (subset of subjects only)
- Compliance assessment (may be performed at any time during the visit)

4 PM (± 30 minutes):

- AE assessment
- Biomicroscopy
- IOP
- Study medication dispensing
- Study medication accountability (may be performed at any time during the visit)

10.4.2. Visit 5/Day 42 ± 3

8 AM (± 30 minutes):

- AE assessment
- Concomitant medication review
- BCVA
- Grading conjunctival hyperemia
- Biomicroscopy
- IOP
- Drop instillation (should occur as close as possible to 15 minutes after IOP measurement but not before 10 minutes after IOP measurement)
- Conduct drop comfort rating following instillation of study medication (≥ 10 minutes after the IOP measurement)

2 hours ± 30 minutes after drop instillation:

- AE assessment
- HR/BP
- Biomicroscopy
- IOP
- Compliance assessment (may be performed at any time during the visit)

4 PM (± 30 minutes):

- AE assessment
- Biomicroscopy
- IOP
- Study medication dispensing
- Study medication accountability (may be performed at any time during the visit)

10.4.3. Visit 6/Last Day of Treatment (Day 84 ± 3)

At Visit 6, subjects will undergo final efficacy and safety assessments and rate the ocular tolerability of study medication.

Visit 6 procedures include the following:

8 AM (± 30 minutes):

- AE assessment
- Concomitant medication review
- Urine pregnancy test (females of childbearing potential only)
- BCVA
- Grading conjunctival hyperemia
- Biomicroscopy
- IOP
- Drop instillation (should occur as close as possible to 15 minutes after IOP measurement, but not before 10 minutes after IOP measurement)
- Conduct drop comfort rating following instillation of study medication (≥ 10 minutes after the IOP measurement)
- Visual field test (may be performed at any point in the visit prior to dilation for ophthalmoscopy)

2 hours ± 30 minutes after drop instillation:

- AE assessment
- HR/BP
- Biomicroscopy
- IOP
- Blood collection for PK assessment (subset of subjects only)
- Compliance assessment (may be performed at any time during the visit)

4 PM (± 30 minutes):

- AE assessment
- Biomicroscopy
- IOP
- Dilated ophthalmoscopy
- Study medication accountability (may be performed at any time during the visit)

10.5. Early Discontinuation Assessment Procedures

If a study subject is discontinued from study medication before Visit 6/Day 84 but after Visit 3/Qualification/Baseline/Day 1, every effort should be taken to perform all the procedures listed for Visit 6 (Section 10.4.3).

If the subject is willing to remain at the site for the 8-hour visit, it should be conducted as specified, but if the subject is not willing to remain for the full duration, the VF test and the dilated ophthalmoscopy should be conducted as the last ophthalmic assessments in the early discontinuation visit.

11. **STATISTICS**

11.1. **General Considerations**

This is a Phase 2 study to evaluate ocular and systemic safety and the efficacy of BTQ-1901-A, BTQ-1901-B, and BTQ-1902 ophthalmic suspensions in comparison to timolol 0.5% ophthalmic solution in subjects with POAG or OHT.

Subjects will be randomized in a 1:1:1:1 ratio into 1 of 4 treatment arms and receive 1 drop in each eye BID, morning, and evening, for 84 days:

- BTQ-1901-A (nebivolol 0.5% ophthalmic suspension) (N = 60)
- BTQ-1901-B (nebivolol 1.0% ophthalmic suspension) (N = 60)
- BTO-1902 (timolol 0.5% ophthalmic suspension) (N = 60)
- Timolol 0.5% ophthalmic solution (N = 60)

A biostatistician will perform statistical analyses as agreed with the Sponsor according to the Statistical Analysis Plan (SAP).

Primary efficacy analysis will be conducted on the per protocol (PP) population. Efficacy analyses will also be conducted on the intent to treat (ITT) population. Safety analyses will be performed using the safety analysis population. Definitions for all of the analysis populations can be found in Section 11.3.

At least one eye must qualify for the study. Even if only one eye meets all inclusion/exclusion criteria, both eyes will be treated. If both eyes qualify, the qualifying eye with the higher IOP at 8:00 AM at Visit 3/Qualification/Baseline will be designated as the study eye. Should the 8:00 AM IOP be the same in both eyes, then the right eye will be designated as the study eye.

At each IOP measurement time point, 2 consecutive IOP measurements of each eye will be performed. If the 2 measurements differ by more than 2 mm Hg, a third measurement will be taken. Mean IOP is calculated as the mean of 2 measurements or as the median of 3 measurements.

A detailed SAP will be finalized prior to database lock. The analysis of continuous and ordinal variables will use the applicable parametric methods (t-test, analysis of variance [ANOVA], and analysis of covariance [ANCOVA], and mixed models for repeated measures [MMRM]). Descriptive statistics will be used to summarize continuous outcomes (number of subjects [N], mean, standard deviation or standard error of the mean, median, maximum, and minimum) and categorical variables (frequency and percentage) at each assessment time point (the time points at which data are collected are specified in the Schedule of Procedures—see Table 2).

The primary efficacy analysis will be the between-group comparison of the mean IOP values in the study eye at each time point at each of the Visit 4/Day 15, Visit 5/Day 42, and Visit 6/Day 84 visits (ie, a total of 9 between-group comparisons).

Final analyses of efficacy will be conducted when all subjects complete Visit 6.

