Drop instillation/ instruction/evaluation					Х	X ¹			X ¹			X ¹		
Drop comfort rating ^m					Х	Х			Х			Х		
Study medication accountability ⁿ					Х			Х			Х			Х
Compliance assessment ^o							Х			Х			Х	

BP = blood pressure; HR = heart rate: IOP = intraocular pressure; IP = investigational product; PK = pharmacokinetics

NOTE: Subjects using ocular hypotensive medications must have undergone the appropriate required washout period prior to Visit 3/Qualification/Baseline. NOTE: If a study subject is discontinued from study medication before Visit 6/Day 84 but after Visit 3/Qualification/Baseline/Day 1, every effort should be taken to perform all the procedures listed for Visit 6/Last Day of Treatment (Section 10.4.3). If the subject is willing to remain at the site for the 8-hour visit, it should be conducted as specified, but if the subject is not willing to remain for the full duration, the VF test and the dilated ophthalmoscopy should be conducted as the last ophthalmic assessments in the early discontinuation visit.

^a Mid-washout safety check for subjects undergoing 28-day washout periods (i.e., prior prostaglandin analogs, rho-associated protein kinase [ROCK] inhibitors, or β-blockers) may be performed at the Investigator's discretion.

^b The window for each time point is ± 30 minutes. For Visit 4/Day 15, Visit 5/Day 42, and Visit 6/Day 84, the 2 h post-dose timepoint will fall around 10:00 AM, but the timing of the IOP measurement is dependent on the time study medication was administered at the site that day and should be 2 hours (± 30 minutes) after the dose was administered.

^c All AEs that occur following consent and until the final study visit (Visit 6/Day 84) should be collected and recorded on the AE eCRF page.

^d Required only for women of childbearing potential. At Visit 3/Qualification/Baseline/Day 1 it must be performed prior to randomization. At Visit 6/Day 84 it may be performed anytime.

^e HR and BP will be measured seated after at least 5 minutes rest. Vital signs may be repeated once, after at least an additional 5 minutes rest in the seated position, if they are out of range.

S	Betaliq, Inc.
Protocol Synopsis BTQ-1901-1902-201	IND 145504

- ^f It is preferred that conjunctival hyperemia be graded as part of the external eye exam performed prior to biomicroscopy.

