7.3. Criteria for Withdrawal from the Study/Criteria for Discontinuation of Study Medication

The following are the criteria for considering withdrawal from the study:

- Withdrawal of subject consent. The subject may request for any reason at any time to be withdrawn from the study.
- Subject lost to follow-up.
- The Sponsor terminates the study (see Section 6.4).

If a subject withdraws from the study, the principal reason for withdrawal will be recorded in the electronic case report form (eCRF). Subjects who are withdrawn will not be replaced.

If a study subject fails to attend a study visit at any point during the study period, every effort should be made to keep the subject in the study and conduct all study visits as scheduled; all attempts to contact the subject must be documented. If the subject relocates during the study period, the clinical research organization (CRO), should be contacted to determine if there is a possibility that the subject could continue at another clinical site.

The following are criteria for considering discontinuation from study medication:

- Pregnancy: If a subject becomes pregnant during the study, the subject will be withdrawn from study medication and followed through the conclusion of the pregnancy (Section 9.5.3).
- Adverse event: A clinically significant or serious AE (SAE) that in the Investigator's or Medical Monitor's judgment, suggests that continued administration of study medication is not in the subject's best interests for safety reasons. Additionally, if an AE requires treatment, the Investigator in consultation with the Medical Monitor may determine that study medication should not be concurrently administered with a required concomitant medication.
- Intraocular pressure in either eye >34 mm Hg during the treatment period.
- Subject request: Subject requests to be withdrawn from study medication.

When possible, a decision to discontinue a subject from study medication should first be discussed with the Medical Monitor. If a subject is discontinued from study medication, every effort should be made to encourage the subject to continue to attend study visits to be followed for safety, rather than withdrawing the subject from the study or, failing that, to perform all early discontinuation assessment procedures at the visit the subject is withdrawn (Section 10.5).

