The study will be observer masked. The study medication will be provided in foil pouches contained in identical-appearing boxes. The pouches will contain 5 mL bottles for the BTQ-1901-A, BTQ-1901-B, or BTQ-1902 treatment arms and 10 mL bottles for the timolol 0.5% treatment arm (see Section 8.1). An unmasked staff member not involved in performing study endpoint-related procedures (i.e., IOP measurement) will be responsible for providing dosing instructions, dispensing study medication, and conducting study medication accountability and dosing compliance assessment. The identity of the study medications will be masked to the Investigator and study personnel responsible for study endpoint-related procedures. Moreover, IOP measurements should be performed by the same Investigator/designee who will be masked to the readout of the tonometer, which will be read and entered into the source documentation (whether electronic or paper) by a second staff member once the Investigator/designee reaches the correct applanation effect in the slit lamp.

8.2.1. **Unmasking During the Study Period**

Should it be necessary to unmask a subject's treatment assignment in case of emergency, the Investigator may obtain the treatment code for a given randomized subject from the IWRS. The treatment code is to be obtained only if a medical emergency exists and knowledge of the medication being taken will influence the medical management of the subject.

The following procedure should be followed:

- 1. The Investigator should attempt to contact the Medical Monitor via phone before unmasking a subject unless it is not possible to do so without risk to the subject.
- 2. The Investigator should document the AE and justification for unmasking in the eCRF.
- 3. If the subject is to be discontinued from study medication, then ALL procedures described in the Early Discontinuation Visit (Section 10.5) should be completed.
- 4. The Investigator should contact the CRO at [contact] within 24 hours with the subject number and details of the AE or SAE and any action taken.

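### The early discontinuation visit calls for all Visit 6 procedures, including a study drop, in subjects already taken off study medication, and neither document exempts the drop

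*Protocol*

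**What the plan says.** **Stopping.** Protocol Section 7.3 lists four criteria for considering discontinuation of study medication: pregnancy, an adverse event, IOP above 34 mm Hg in either eye, and subject request. For pregnancy the wording is mandatory: "the subject will be withdrawn from study medication and followed through the conclusion of the pregnancy". Section 9.5.3 repeats it. For a clinically significant or serious adverse event, the test is whether the investigator or Medical Monitor judges that it "suggests that continued administration of study medication is not in the subject's best interests for safety reasons".

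**What happens next.** Section 7.3 prefers that the subject keeps attending visits for safety follow-up. Failing that, the early discontinuation procedures of Section 10.5 are done at the visit of withdrawal. Section 10.5 then says "every effort should be taken to perform all the procedures listed for Visit 6 (Section 10.4.3". The note under Table 2 says "every effort should be taken to perform all the procedures listed for Visit 6/Last Day of Treatment (Section 10.4.3", and SAP Table 1 carries the same note. After emergency unmasking, Section 8.2.1 step 3 says: "If the subject is to be discontinued from study medication, then ALL procedures described in the Early Discontinuation Visit (Section 10.5) should be completed".

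**What the Visit 6 list contains.** Section 10.4.3 includes "Drop instillation (should occur as close as possible to 15 minutes after IOP measurement, but not before 10 minutes after IOP measurement" and then "Conduct drop comfort rating following instillation of study medication". Its second block (heart rate and blood pressure, biomicroscopy, IOP and, in the pharmacokinetic subset, a blood draw) is timed from the drop.

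**The concern.** Section 10.5 applies only to subjects who have been taken off study medication, yet the list it calls in begins the day with a dose of that medication. For a subject stopped for pregnancy or a suspected beta-blocker reaction, the stopping text and the procedure list point in opposite directions. Protocol Section 4 names bronchospasm, decreased heart rate and congestive heart failure among the systemic effects of the class, and says these formulations have not been evaluated in clinical trials before. The step that follows emergency unmasking is where another dose would be least wanted.

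A related conflict affects subjects who stop drug but keep attending, as Section 7.3 encourages. Section 10.4 requires anyone who missed the previous evening's dose to be rescheduled, even outside the visit window. An off-drug subject can never meet that condition, so the literal rule blocks the follow-up that Section 7.3 asks for. Section 8.5.2 also has the morning dose given on site at each of these visits.

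**Working it through.** There is no planned figure to reproduce. The check is to follow the cross-references and look for an exemption.

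1. **Who is covered.** Section 10.5 covers any subject discontinued from study medication after Visit 3 and before Visit 6. That takes in all four criteria in Section 7.3.
2. **What is called in.** Section 10.5 and the Table 2 note point directly to Section 10.4.3. Section 8.2.1 step 3 points to Section 10.5 and so to the same list.
3. **Is the drop study medication?** Yes. The comfort rating in Section 10.4.3 names it as such, and Section 8.5.2 has the morning dose given on site at Visits 4, 5 and 6.
4. **Is it exempted?** Section 10.5 makes one adjustment: if the subject will not stay all day, visual field testing and dilated ophthalmoscopy come last. For a subject who will stay, it asks for the visit as specified. Section 8.5.3 ends dispensing at Visit 6 but not the in-clinic drop. The SAP only repeats the note, and its Section 5.1 defers to the protocol. Exemptions found: none in the protocol, none in the SAP.
5. **Literal exposure.** Section 8.5.2 gives 1 drop per eye: 1 × 2 eyes = 2 drops, one bilateral dose per affected subject.
6. **What depends on the drop.** Without a dose, the comfort rating has no object and the pharmacokinetic draw (planned in 40 of the 240 subjects) has no post-dose meaning. Heart rate and blood pressure, biomicroscopy and IOP can still be done, but they need a new clock time. Table 2 footnote b says that "the 2 h post-dose timepoint will fall around 10:00 AM", but it goes on to tie the IOP reading to when the dose was given that day. So about 10:00 AM is a sensible substitute that has to be written in. There is a precedent at Visit 3, where the 10 AM set precedes the first drop in the 4 PM block.
7. **Subjects stopped during a visit.** Section 7.3 places the procedures at the visit of withdrawal. A subject stopped at the 2-hour or 4 PM assessment, for example for IOP above 34 mm Hg, has already had that day's dose. For that subject the comfort rating and the draw are legitimate.
8. **Efficacy.** The primary model (SAP 9.1) and the non-inferiority rule (SAP 7.5) are set on the nine scheduled time points at Visits 4, 5 and 6. Neither refers to the early discontinuation visit, and nothing in the documents shows an estimate changing with the extra drop.

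**The case against.** The strongest reply is that no site would read the text this way. Section 10.5 opens with a subject who is off drug, its heading speaks of assessments, and a dose is treatment. It asks for every effort, which is not an order to dose. Only Section 8.2.1 is firmer, and it leads back to Section 10.5. The Study Manual, which is not among the documents, may settle the matter. Much of this stands, and it is why the point is minor. It does not make the text consistent. Section 13.7 tells investigators not to deviate except in a medical emergency, and pregnancy or a subject's request is not in itself one. A site that sensibly withholds the drop therefore omits a listed procedure.

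It can also be said that Section 7.3 lists criteria for considering discontinuation, so calling them all stop rules overstates them. That is right: only pregnancy is worded as automatic. But Section 10.5 applies once the decision has been made, whatever the reason.

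On Section 10.4, the evening-dose check is plainly meant to standardise IOP timing in subjects on drug. That is its likely purpose, but the text does not limit it to them.

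A reader might infer that everything else at Visit 6 can go ahead unchanged without the drop. The documents do not support that, because footnote b ties the 2-hour IOP to the dose time.

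**Conclusion.** This is a minor internal contradiction. Section 10.5, the Table 2 note with its SAP copy and, by reference, Section 8.2.1 step 3 call for a study drop in subjects already discontinued from study medication. That conflicts with Sections 7.3 and 9.5.3. The conflict is with a mandatory rule for pregnancy and with a clinical judgment for adverse events. The literal size is one bilateral dose per affected subject; the number affected is not given.

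Two stronger readings are tempting. One is that stopped subjects will in practice be re-dosed. The documents show only that the wording allows it, and investigators would probably withhold the drop. The other is that the trial's efficacy conclusions are at risk. Nothing in the protocol or SAP supports that: no efficacy estimate or decision rule is affected.

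The conclusion rests on the protocol and SAP alone and would soften if the Study Manual exempts the drop.

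**What to change.** In Section 10.5 and the Table 2 note, add:

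> No study medication is to be instilled after the decision to discontinue. The drop comfort rating and post-dose PK draw are done only if that day's on-site dose was taken before the decision; otherwise the 2-hour assessments are done at about 10:00 AM.

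Tying the rule to the moment of the decision matters. A blanket exclusion would discard valid comfort and pharmacokinetic data from subjects stopped later on a day when they had already dosed. Section 8.2.1 step 3 then follows by cross-reference.

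In Section 10.4, add that the evening-dose check, the rescheduling rule and the on-site dose apply only to subjects still on study medication.

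The copied note in the SAP can be aligned at its next version; no analysis changes. The cost is a few sentences, with no added visits, procedures or subjects. It is still a protocol amendment, which Section 13.7 requires to go to the FDA and be approved by the IRB before use, so bundling it with the next amendment is proportionate.
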